5.0 DATA ANALYSIS AND STATISTICAL CONSIDERATIONS

Data collected in this phase are purely descriptive and no formal analysis is planned.

6.0 DATA SAFETY AND MONITORING

- 6.1 Data and Safety Monitoring Board (DSMB). We will continue to use the Data Safety Monitoring Board (DSMB) for the Department of Psychiatry as a third-party oversight committee as we have done for the DBS for TRD study.
- 6.2 Frequency of meetings/review. The frequency of DSMB review for this protocol will follow recommendations from CPHS based on the assessed risk status of the study. Currently, it is expected that the DSMB will meet annually.
- 6.3 This protocol will be submitted to the DSMB simultaneously with this initial submission to CPHS. The DSMB will review the research protocol and plans for data and safety monitoring. The DSMB will review a report from the study's data manager that includes the following information: the number of participants who signed consent forms for the study and were subsequently randomized to study arms, the number of post-randomization dropouts, the reasons for withdrawal from the study, and any safety concerns, adverse events, an up-to-date consent form, and measures taken to protect confidentiality (e.g., data and tape storage, use of coded ID numbers, etc.). The DSMB will also review the Principal Investigator's summary of any new data or evidence that might alter the risk/benefit ratio for participating in the study (e.g., newly published studies, etc.). After reviewing this information, the DSMB will issue its own report summarizing any serious and unexpected adverse events or other unanticipated problems that involve risk to study participants, and whether these appear related to the study-based interventions or research assessment protocols.
- 6.4 There will be regular, ongoing communication between the PI, CPHS, and the DSMB. The PI will take responsibility for reporting any serious and unexpected adverse events or other unanticipated study problems to CPHS within 24 hours, according to standard regulations. A copy of each report will be sent to the DSMB. Actions taken by CPHS in response to adverse event reports will be immediately reported to the DSMB, which will review all serious adverse events as they arise. DSMB reports will be shared with CPHS.
- 6.5 A Serious Adverse Event (SAE) in this study will be defined as an event that results in death, is life-threatening, requires hospitalization or prolongation of existing hospitalization, or results in persistent or significant disability or incapacity. The degree of probable relation between study procedures and the SAE will be carefully evaluated and documented.
- 6.6 Unexpected adverse events in this study will be defined as any adverse events for which the nature and severity are not consistent with expected adverse events resulting from the surgery, pre- or post-operative evaluation, or deep brain stimulation.

6.7 The DSMB will have the authority to stop the study at any point.

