A second sham-controlled pilot study at Emory University assessed the safety and efficacy of bilateral SCC DBS in 10 TRD patients with major depressive disorder (MDD) and 7 TRD patients with bipolar II disorder (BP). [name] was the lead psychiatrist on this study. Rates of response ($\geq 50\%$ decreased in depression severity from baseline) were 41% at 6 months, 36% at 1 year and 92% at 2 years following onset of chronic stimulation. Rates of remission (virtually no depressive symptoms) were 18% at 6 months, 36% at 1 year and 58% at 2 years following onset of chronic stimulation. There was a very modest but statistically significant decrease in depression severity following 4 weeks of sham stimulation, but this was largely accounted for by a decrease in depression severity following surgery but prior to the onset of sham stimulation. In three patients in whom blinded discontinuation was performed after 24 weeks of active stimulation, all had a full return of depressive symptoms within two weeks and antidepressant benefit returned with re-initiation of stimulation. There was only one patient who experienced a serious adverse event (infection requiring removal of the system) related to surgery. There were no adverse events associated with acute or chronic stimulation. In this study, a longer duration of a euthymic (no depression) period since illness onset, fewer adequate antidepressant treatments in the current episode, fewer lifetime psychotropic medications and fewer depressive episodes each predicted response/remission at various time points in the study. It was also demonstrated that functional connectivity of the BA25/SCC region (derived from pre-operative resting state functional magnetic resonance imaging [rfMRI] data) predicted 6 month treatment response. If validated, this would support using clinical variables related to illness stability (number of episodes, time between episodes and number of treatments) as well as pre-operative rfMRI to help with patient selection if SCC DBS is introduced clinically.

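### Does section 6.4 leave the DSMB without prompt sight of serious adverse events that are judged expected?

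*Combined protocol and SAP*

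**What the plan says.** Section 6.4 contains two statements of different scope. The first is the investigator's duty to the ethics committee: "The PI will take responsibility for reporting any serious and unexpected adverse events or other unanticipated study problems to CPHS within 24 hours". It is followed by "A copy of each report will be sent to the DSMB". The second describes the board's own task, at the end of a sentence about telling it at once of any ethics committee action on adverse event reports: "which will review all serious adverse events as they arise". The section opens with a general undertaking that the investigator, the committee and the board will stay in continuing contact.

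Seriousness is defined by outcome in section 6.5: "A Serious Adverse Event (SAE) in this study will be defined as an event that results in death, is life-threatening, requires hospitalization", and so on. Section 6.6 calls an event unexpected when "the nature and severity are not consistent with expected adverse events resulting from the surgery, pre- or post-operative evaluation, or deep brain stimulation". The protocol gives no list of expected events.

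Section 6.1 carries the board over from the parent study: "We will continue to use the Data Safety Monitoring Board (DSMB) for the Department of Psychiatry as a third-party oversight committee". Section 6.2 expects it to meet once a year, subject to the committee's recommendation. Section 6.3 has it review a data manager's report that covers adverse events without regard to expectedness. That report is also to give numbers randomized and numbers lost after randomization, although this protocol randomizes nobody.

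**The concern.** The board is to look at every serious event when it happens, yet the one report described as reaching it at that time carries a filter for unexpectedness. Serious events in line with the known effects of surgery, perioperative evaluation or stimulation fall outside that filter. These are the intervention's own recognized harms. The Introduction gives an example from the earlier pilot at another center: "There was only one patient who experienced a serious adverse event (infection requiring removal of the system) related to surgery".

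If staff worked only from the 24-hour rule, an event of this kind that was judged expected would first reach the board in the periodic report. Long-term safety is part of the single specific aim (section 2.0), and section 6.7 lets the board stop the study at any time, so a late view of known harms would weaken that oversight. The randomization counts in section 6.3 add to the impression that the monitoring text was not fully adapted to this study.

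**Working it through.** No sample size, power or error rate is involved, so the check compares the set of events the board must review with the set it is said to receive.

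1. **Review duty (6.4).** All serious adverse events, expected or unexpected, as they occur.
2. **Event-triggered report (6.4).** Events that are both serious and unexpected, plus other unanticipated problems; to the committee in 24 hours, copied to the board. Notice of committee action is also immediate, but it depends on a report having reached the committee.
3. **Difference.** Item 1 minus item 2 leaves serious events judged expected under 6.6. A serious event from an unrelated illness is not in this remainder: it does not match the expected effects of surgery, evaluation or stimulation, so it takes the 24-hour route.
4. **Periodic route (6.3).** The remainder still reaches the board in the data manager's report, which lists adverse events of every kind.

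*Longest wait for the remainder.* Counting from when the investigator learns of the event, and assuming that nothing is forwarded and the event falls just after a review, the wait is one review interval: about 12 months at the annual frequency in 6.2, against a 24-hour committee report with a copy to the board for unexpected events. Section 4.0 schedules patient contact only every 12 months, apart from weekly monitoring for 12 weeks after explantation or switch-off. The time before an event becomes known may therefore be as long as any routing delay.

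*Size of the affected class.* The documents give no rate of expected serious events for this phase. The pilot had 10 + 7 = 17 patients and one with a surgery-related serious event: 1/17 = 5.9%. That illustrates the type of event and cannot be carried over as a rate. Section 3.1 requires patients to have already received DBS, this protocol schedules no implantation, and the only surgery it mentions is explantation at the patient's choice (section 4.0). On stimulation itself, the Introduction says of the pilot: "There were no adverse events associated with acute or chronic stimulation".

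*Can both statements in 6.4 be met?* Yes. The 24-hour rule sets a minimum for the committee and adds a copy for the board; it does not say that the board receives nothing else. The review duty can be met only if expected serious events are forwarded too. Meeting both means forwarding them, and neither statement forbids it.

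*Section 6.3 counts.* With no randomization there is nothing to enter for numbers randomized or lost after randomization. The same list still supplies the number who signed consent and the reasons for withdrawal, which describe a cohort of five.

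**The case for a change.** The strongest case for a change is that a duty without a named sender tends not to be carried out. A coordinator working from the written route would send the 24-hour report and could hold everything else for the annual report. The events held back would be the known harms of the device and surgery, and with no list of expected events the classification is left to judgment. The promise of continuing contact names no event, sender or time. The board's own report in 6.3 is framed around serious and unexpected events, so it does not clearly fill the space. One sentence would settle the matter at almost no cost.

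Much of this stands as a comment on drafting: the two scopes differ, and no one is named. It does not show a failure of routing. It assumes that staff act on one sentence of 6.4 and disregard another in the same section. It also assumes that a departmental board already serving the parent study has no working arrangement for receiving serious events, which these documents cannot show either way. The framing in 6.3 supports a second reading as well: the clause on all serious events may mean all those reported to the committee, in which case there is no mismatch. The literal reading is at least as natural, so this does not dispose of the point, but it makes the intended scope uncertain.

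**Conclusion.** The difference in wording is real, but no change to the plan is called for. Section 6.4 already obliges the board to review every serious event as it arises, and that implies that the board is told. The gap is the name of a sender and a trigger, a working detail that a study team and an established departmental board can fill sensibly. An added sentence would make the duty more explicit without creating one.

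The most that could go wrong is a delay of about 12 months in the board seeing a serious event judged expected. That requires annual review, an event just after a review, and no forwarding despite the review duty. Such events would still appear in the periodic report. With five patients and, under section 5.0, no formal analysis, no estimate or conclusion is affected. The randomization terms in 6.3 are inapplicable text, and removing them would be an editorial correction.

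This rests on staff reading 6.4 as a whole and on the board being able to receive events between meetings, as its review duty presupposes. The documents do not show the board's own procedures.
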